#### **TRIAL SCHEMA**

## **CASSETTE** patient pathway

## **SCHEDULE OF OBSERVATIONS AND PROCEDURES**

## **KIDNEY STONE (KS) PATIENTS**

		Timepoint						
	Responsibility*1	Screening	Surgery 1	4-7 days post- Surgery 1	Within 24 hrs prior to surgery 2	Surgery 2	2-3 weeks post-Surgery 2	Qualitative interview (optional timepoint)
		(Day 0) Up to 8 weeks before surgery	Day of novel ureteric stent insertion	4-7 days post novel ureteric stent insertion	Within 24 hours prior to the novel ureteric stent removal	Day of removal of novel ureteric stent	2-3 weeks post novel ureteric stent removal	Within first month of stent removal for participants (Up to 1 month from recruitment end for clinicians)
Screening of surgery lists and								
sending PIS to potentially eligible patients	Site	x						
Informed Consent*2	Site	х	Х					
Eligibility evaluation*2	Site	х	х					
Medical History (Clinical team may review medical history to check eligibility criteria)	Site	x	x					
Check for Adverse Events/Device Deficiencies )	Site		x			х	x*3	x
Registration*2	Site	х	х					
Physical Exam*2	Site	х	Х					
KS Patient Questionnaire – BASELINE	Patient		х					
KS Patient In Situ Questionnaire	Patient			х	Х			
KS Patient Questionnaire (Post- surgery)	Patient						х	
Investigational device insertion	Study doctor		х					
Investigational device removal	Study doctor					х		
Sample collection (urine and removed novel ureteric stent)	Site					х		
Laboratory Tests (pre-op anaesthetic tests) – as required by the clinical team*4	Site	х						

CTU/FORM/5321 – Clinical Investigation Plan template for Clinical Investigations of Medical Devices (excl. IVDD) Version 1 14-DEC-2023

Endpoint analysis – weighing, cell culture, imaging	Microbiology research lab/imaging unit			х	
Endpoint analysis - Flow rate	Bioengineering lab			х	
Safety blood test (eGFR, Creatinine) – (when clinically needed) *4	Site			х	
Pregnancy Test*4	Site	х		х	
Qualitative Interview (optional)	Qualitative researcher				х

**NB:** The Participant/legal representative is free to withdraw consent at any time without providing a reason. When withdrawn, the participant will continue to receive standard clinical care. Follow up data will continue to be collected (unless the participant/legal representative has specifically stated that they do not want this to happen).

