#### 1 INTRODUCTION

#### 1.1 BACKGROUND

Ureteric stents and catheters are deployed clinically as temporary measures to restore urinary drainage, in patients with kidney stones, tumours and strictures. Prevalence of these increases with age [1]–[4]. Device-associated encrustation and biofilm formation (E&B) are key complications, leading to urinary tract infections (UTIs) in >90% of stents [5], causing stent blockage and favouring development of antibiotic resistance.

UTIs are a significant cause of morbidity, especially among the elderly population, with 4,835 deaths in England and Wales reported in 2012 [6]. The National Institute for Health Research (NIHR, 2016) reported that 1-3% of all primary care consultations concern UTI-related symptoms, leading to 13.7% of antibiotic prescriptions globally. The report also revealed that >92m people globally are diagnosed with UTIs annually [7].

Urological device-associated infections significantly compromise patient' quality of life and the effectiveness of services, imposing a £2.5b annual burden on the NHS [8]. Patients' exposure to hospital environment and general anaesthetic use impact on Quality-of-Life (QoL), resulting in unnecessary hospital bed-nights. We have developed a novel urological stent associated with significantly reduced particle deposition, potentially extending the stent's lifetime, resulting in reduced hospitalisation and improved QoL.

Urological stents and catheters often lead to inflammation, causing pain and infection in the urinary tract [7]. Moreover, 80% of stents are associated with pain, negatively impacting on QoL [9] and mental health. Offering novel designs with significantly lower E&B leads to a reduction in UTIs and improves QoL. Reducing hospital admissions (from 3 to 1 per patient, annually) would free >100,000 bed-nights, allowing the elderly to regain independence. Our proposed research could have a significant impact towards fulfilling the 'healthy ageing' Grand Challenge. Additionally, the novel stent reduces prevalence of infections and therefore, of antibiotic prescriptions contributing to the Global Antimicrobial Resistance (AMR) challenge.

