#### 6.5 TRIAL PROCEDURES – KIDNEY STONE PATIENTS

#### 6.5.1 Day of Surgery 1

- The clinical team will take informed consent (if not already received)
- Assessment of patient eligibility (including standard of care pregnancy test required to confirm eligibility)
- Patient history assessment
- Physical Exam
- Check for Adverse Events/Device Deficiencies
- Register patient onto the database
- Prior to novel ureteric stent insertion, patients will be asked to complete CASSETTE (Kidney Stone)
  Patient Questionnaire BASELINE\* questionnaire on paper

\*Kidney stone baseline (no current stent in place) questionnaires includes:

- EQ5D-5L
- Subject demographics
- Short Version Stent Quality of Life (no current stent in place)
- USI-QoL Stone disease

\*Kidney stone baseline (current stent in place) questionnaire includes:

- EQ5D-5L
- Ureteric Stent Symptoms Questionnaire (with a stent in place) [USSQ]
- Subject demographics
- Short Version Stent Quality of Life (stent in place)
- USI-QoL Stone disease

The clinician will then perform surgery (for the purpose of this study this is called surgery 1) and inserts the novel ureteric stent (this may be a replacement of pre-existing stent). Any adverse events occurring during the surgery (either as a result of the removal of the old stent, or the insertion of the novel stent), as well as any device deficiencies occurring with the novel stent, must be recorded on the database.

#### 6.5.2 4-7 days post-Surgery 1

Patients will be asked to complete CASSETTE (Kidney Stone) Patient In Situ Questionnaire — 4-7 days after Surgery 1\* questionnaire online, or if completed on paper, the questionnaires will be returned to the site team using a freepost envelope. (Sites can also collect questionnaires over the phone with the participant if the participant choses this option)

\*Kidney stone in situ (4-7 days after surgery 1) questionnaire includes:

- EQ5D-5L
- Antibiotics/Hospitalisation
- Short Version Stent Quality of Life
- USI-QoL Stone disease
- Ureteric Stent Symptoms Questionnaire (with a stent in place) [USSQ]

#### 6.5.3 Within 24hrs prior to Surgery 2

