Patients will be asked to complete CASSETTE (Kidney Stone) Patient In Situ Questionnaire - Surgery 2\* questionnaire online, or if completed on paper, the participants should bring the questionnaires with them to the day of removal surgery. (Sites can also collect questionnaires over the phone with the participant if the participant choses this option)

\*Kidney stone in situ (Surgery 2) questionnaire includes:

- EQ5D-5L
- Antibiotics/Hospitalisation
- Short Version Stent Quality of Life

CTU/FORM/5321 – Clinical Investigation Plan template for Clinical Investigations of Medical Devices (excl. IVDD) Version 1 14-DEC-2023

- USI-QoL Stone disease
- Ureteric Stent Symptoms Questionnaire (with a stent in place) [USSQ]

#### 6.5.4 Day of Surgery 2

The clinical team performs surgery 2 and removes the experimental (novel) ureteric stent (and replaces with standard of care ureteric stent as applicable). For kidney stone patients, this will take place approximately 4 weeks after insertion. The novel ureteric stents can be removed earlier if deemed necessary by the treating clinician. At this stage, the clinical team will collect information relating to any adverse events and device deficiencies and record these on the database.

The clinical team will collect a urine sample and the experimental (novel) ureteric stent following the procedures detailed in the laboratory manual. The clinical team will perform any standard of care procedures as required, including performing safety blood tests. These will be detailed in the patients' medical notes and will only be collected as part of the trial data if clinically relevant.

## 6.5.5 Two to three (2-3) weeks post-Surgery 2

Patients will be asked to complete CASSETTE (Kidney Stone) Patient Questionnaire – Post Removal surgery\* questionnaire online or if completed on paper, the questionnaires will be returned to the site team using a freepost envelope.

\*Kidney stone (post-removal surgery) questionnaire includes:

- EQ5D-5L
- Antibiotics/Hospitalisation
- Short Version Stent Quality of Life
- USI-QoL Stone disease
- Ureteric Stent Symptoms Questionnaire (after stent removed) [USSQ]

questionnaires over the phone with the participant if the participant choses this option.

The site research team will also contact the patient by telephone to collect any AEs/DDs as appropriate 1-3 weeks post-surgery 2. If the phone call is to happen at week 2 or 3, then sites can also collect the

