TRIAL PROCEDURES – ONCOLOGY PATIENTS

#### 6.6.1 Day of Surgery 1

6.6

- The clinical team will take informed consent (if not already received)
- Assessment of patient eligibility (including standard of care pregnancy test required to confirm eligibility)
- Patient history assessment
- Physical Exam
- Check for Adverse Events/Device Deficiencies
- Register patient onto the database
- Prior to novel ureteric stent insertion, patients will be asked to complete CASSETTE (Oncology)
   Patient Questionnaire BASELINE\* questionnaire on paper

\*Oncology baseline (no current stent in place) questionnaires includes:

- Subject demographics
- Short Version Stent Quality of Life (no current stent in place)
- EQ-5D-5L

\*Oncology baseline (current stent in place) questionnaire includes:

- Subject demographics
- Short Version Stent Quality of Life (stent in place)
- EO-5D-5L
- Ureteric Stent Symptoms Questionnaire (in-situ) [USSQ]

CTU/FORM/5321 – Clinical Investigation Plan template for Clinical Investigations of Medical Devices (excl. IVDD) Version 1 14-DEC-2023 The clinician will then perform surgery (for the purpose of this study this is called surgery 1) and inserts the novel ureteric stent (this may be a replacement of pre-existing stent). Any adverse events occurring during the surgery (either as a result of the removal of the old stent, or the insertion of the novel stent), as well as any device deficiencies occurring with the novel stent, must be recorded on the database.

#### 6.6.2 4-7 days post-Surgery 1

Patients will be asked to complete CASSETTE (Oncology) Patient In Situ Questionnaire – 4-7 days after Surgery  $1^*$  questionnaire online, or if completed on paper, the questionnaires will be returned to the site team using a freepost envelope. (Sites can also collect questionnaires over the phone with the participant if the participant choses this option)

\*Oncology in situ (4-7 days after surgery) questionnaire includes:

- Antibiotics/Hospitalisation
- Short Version Stent Quality of Life
- EQ-5D-5L
- Ureteric Stent Symptoms Questionnaire (with a stent in place) [USSQ]

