# 6.6.3 Halfway between Surgery 1 and Surgery 2 (mid-point to be based on planned removal/replacement date +/- 1 week)

Patients will be asked to complete CASSETTE (Oncology) Patient In-Situ Questionnaire - Halfway\* questionnaire online, or if completed on paper, the questionnaires will be returned to the site team using a freepost envelope.

\*Oncology in situ (Halfway) questionnaire includes:

- Antibiotics/Hospitalisation
- Short Version Stent Quality of Life
- EQ-5D-5L
- Ureteric Stent Symptoms Questionnaire (with a stent in place) [USSQ]

The site research team will also contact the patient by telephone to collect any AEs/DDs as appropriate. Sites can also collect the questionnaires over the phone with the participant at this time point, if the participant choses this option.

#### 6.6.4 Within 24hrs prior to Surgery 2

Patients will be asked to complete CASSETTE (Oncology) Patient In-Situ Questionnaire - Surgery 2\* questionnaire online, or if completed on paper, the participants should bring the questionnaires with them to the day of removal surgery. (Sites can also collect questionnaires over the phone with the participant if the participant choses this option)

\*Oncology in situ (Surgery 2) questionnaire includes:

- Antibiotics/Hospitalisation
- Short Version Stent Quality of Life
- EQ-5D-5L
- Ureteric Stent Symptoms Questionnaire (with a stent in place) [USSQ]

## 6.6.5 Day of Surgery 2

The clinical team performs surgery and removes the novel ureteric stent (a standard of care ureteric stent may be replaced during this surgery as required). For oncology patients, this will take place approximately 25 weeks after insertion. The novel ureteric stents can be removed earlier if deemed necessary by the treating clinician. The novel ureteric stents can be removed earlier if deemed necessary by the treating clinician. At this stage, the clinical team will collect information relating to any adverse events and device deficiencies and record these on the database.

The clinical team will collect a urine sample and the experimental (novel) ureteric stent following the

procedures detailed in the laboratory manual. These will be analysed. The clinical team will perform any standard of care procedures as required, including performing safety blood tests. These will be detailed in the patients' medical notes and will only be collected as part of the trial data if clinically relevant.

#### 6.6.6 Two to three (2-3) weeks post-Surgery 2

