## 8.5 STATISTICAL ANALYSIS PLAN (SAP)

The primary analysis will be an estimate of the proportions (and associated 95% Wilson method confidence intervals [21] of stent failure, presented by patient group (oncology or kidney patients). This data will also be compared against data from those using existing stents (UPPEUS); an odds ratio and two-sided 95% confidence interval will be produced for oncology patients and kidney stone patients separately to compare the proportions of stent failure according to stent type. Each element of the composite outcome will also be presented and compared as a secondary analysis, using the same methods as the primary endpoint. The EQ-5D-5L, USSQ, and USI-QoL scores will be summarised with mean, SD, median, and IRQ. No corrections for multiple testing will be applied, and no threshold is set for the p-value as the study is not designed to formally compare groups. Descriptive statistics will be presented for baseline measures and the other secondary outcomes:

- Dwell time (mean, standard deviation) and number of stents required over clinically meaningful period
- Patients who: experience urinary symptoms (for any and for each symptom), use antibiotics, are readmitted, have urosepsis, die (frequency and percentage)
- Questionnaires at each time point (mean and standard deviation or median and quartiles)
- Laboratory and microbiology data at each time point (mean and standard deviation or median and quartiles)

Adverse events and Serious Adverse Events for the full population will be summarised descriptively for both groups. Overall AEs will be also summarised by CTCAE Grade for each group. No statistical comparisons will be undertaken on this data.

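### The secondary infection outcomes have no structured pre-insertion value: the Antibiotics/Hospitalisation form is missing from all four baseline packs and study urine is taken only at Surgery 2

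*Protocol*

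**What the plan says.** **Outcomes.** The endpoint table in protocol section 2.5 lists infections under the objective of finding out whether clinical outcomes are better with the novel stent. They are summarised as numbers and percentages with antibiotic use, readmission, urosepsis, ITU and death, and as an infection count per unit of stent time. CFU counts per organism appear separately, under encrustation and biofilm. Section 8.5 makes the infection outcomes descriptive and adds "Laboratory and microbiology data at each time point (mean and standard deviation or median and quartiles".

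**Samples.** The kidney stone schedule has one row, "Sample collection (urine and removed novel ureteric stent", marked once. Section 6.5.4 (day of Surgery 2) says: "The clinical team will collect a urine sample and the experimental (novel) ureteric stent following the procedures detailed in the laboratory manual". Section 6.6.5 has the same instruction for oncology: "The clinical team will collect a urine sample and the experimental (novel) ureteric stent following the" manual's procedures. No study sample is listed at screening or Surgery 1, and a stent taken out at Surgery 1 is not collected.

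**Questionnaires.** The pack introduced by "Kidney stone baseline (current stent in place) questionnaire includes" contains EQ5D-5L, USSQ, demographics, the short stent quality-of-life form and USI-QoL. The one introduced by "Oncology baseline (current stent in place) questionnaire includes" contains demographics, the short stent form, EQ-5D-5L and USSQ. The versions for patients without a stent in place drop the USSQ. Antibiotics/Hospitalisation first appears after insertion, in the pack introduced by "Kidney stone in situ (4-7 days after surgery 1) questionnaire includes" and in its oncology counterpart in 6.6.2.

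**The concern.** Inclusion criterion 3 requires earlier experience of a ureteric stent, and sections 6.5.1 and 6.6.1 allow Surgery 1 to be an exchange of a stent already in place. No exclusion criterion removes patients with current infection or bacteriuria. The background section itself describes encrustation and biofilm as "leading to urinary tract infections (UTIs) in >90% of stents [5".

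Some participants may therefore come to Surgery 1 on antibiotics, recently admitted, or with colonised urine. If that state is not recorded in a structured way, an antibiotic course reported at 4-7 days, or an organism grown from urine at removal, may belong to the period before the novel stent.

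At stake is the interpretation of the outcomes meant to show whether infection-related results are better. The design has no control group, and section 8.5 compares only stent failure and its components with UPPEUS. The infection outcomes thus have neither a stated comparator nor a value from the same patient before insertion. An unseen SAP cannot repair this, because it cannot recover data that were never collected.

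**Working it through.** This is mainly a check of what is collected and when.

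**1. Antibiotics/Hospitalisation form, pack by pack (sections 6.5 and 6.6)**

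| Cohort | Baseline packs with the form | Later packs with the form |
|---|---|---|
| Kidney stone | 0 of 2 (6.5.1) | 3 of 3 (6.5.2, 6.5.3, 6.5.5) |
| Oncology | 0 of 2 (6.6.1) | 4 of 4 (6.6.2, 6.6.3, 6.6.4, 6.6.6) |
| Total | 0 of 4 | 7 of 7 |

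Quality of life is treated differently: EQ-5D-5L, the short stent form and, with a stent in place, the USSQ are all taken before insertion. Infection history is what is left out.

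**2. Microbiology time points.** Sections 6.5.4 and 6.6.5 give one, Surgery 2. In the oncology schedule the sampling mark seems to sit one column early. That may come from reading the table, and the text of 6.6.5 settles it. The plural wording in 8.5 has only one microbiology time point to draw on.

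**3. Other sources of a baseline.** Pre-operative tests are done as the clinical team requires and reach the database only if clinically relevant (schedule footnote 4). Section 7.5.2 sends known pre-existing conditions to the Medical History eCRF and keeps them out of the adverse event count unless they worsen. Neither gives a systematic antibiotic or admission history, or a culture.

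**4. Can the distortion be sized?** Not from the documents. As an illustration only, let r be the true share newly colonised, s the share with a stent in place at Surgery 1, and c the share of those whose earlier colonisation persists. The share seen positive at removal is r + (1 - r) × s × c. All inputs are assumed, with r = 20% and 25 patients per cohort:

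- s = 0: 20%, so no excess from an in-situ stent.
- s = 25%, c = 30%: 0.20 + 0.80 × 0.075 = 26%, or 1.5 extra positives.
- s = 50%, c = 60%: 0.20 + 0.80 × 0.30 = 44%, or 6 extra.
- s = 100%, c = 90%: 0.20 + 0.80 × 0.90 = 92%, or 18 extra.

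The range from 0 to 18 shows that the answer rests on s and c, which the protocol does not give. The formula covers only the route that raises counts. Antibiotics already running at insertion could lower them.

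**5. Effect on the plan's own figure.** The only stated precision is about ±13% (n = 50) and ±18% (n = 25), for stent failure. The Wilson half-width is z√(p(1-p)/n + z²/4n²) / (1 + z²/n). At p = 0.5 it gives 13.4% and 18.2%, so the figure is reproduced. It does not depend on this point.

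**The case against.** **Loose wording in 8.5.** The bullet also covers laboratory data, and the schedules place laboratory tests at screening and Surgery 2. The plural fits part of the bullet, and microbiology can still be summarised at its one time point. This stands: it is a wording correction, not an impossible analysis.

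**The device has a baseline.** The stent is sterile and single use, so whatever is found on its surface formed during its dwell. This stands for biofilm on the stent. It does not cover urine colonisation or earlier antibiotic use and admissions.

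**Known infections are handled.** Medical history is reviewed, and pre-existing conditions stay out of the adverse event count. This stands for recognised infections. It does not reach unrecognised bacteriuria or antibiotic use reported by questionnaire.

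**The form is not shown.** If it asks only about events since surgery, earlier courses may not be counted. That would reduce misattribution, but there would still be no pre-insertion value to set the counts against.

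**A stronger reading is tempting.** From the figure of over 90% in the background, a reader might infer that most participants are already infected at insertion and that the results are biased against the novel stent. The documents do not support this. That figure concerns UTIs with stents, not culture results at Surgery 1. The share with a stent in place is not given, and prior experience carries no time limit. Bias against the device also needs a reference, and none is set for these outcomes.

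**Conclusion.** The concern holds in a limited form. Antibiotic use, readmission and infections per unit of stent time have no structured pre-insertion value, and urine is cultured only at removal. Events or colonisation already present at insertion cannot be reliably separated from those that arise with the novel stent.

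The size is unknown and so is the direction. The problem bites mainly in participants with a stent in place at Surgery 1. The conclusion assumes that the packs contain only the components listed and that the Laboratory Manual, which is not at hand, adds no earlier sample; the visit sections call on it only for Surgery 2.

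The primary endpoint, its comparison with UPPEUS and the sample size are untouched. This is a cheap improvement to secondary descriptive outcomes, not a flaw that threatens the trial's main result.

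**What to change.** 1. Add the existing Antibiotics/Hospitalisation section, including current antibiotics, to the four baseline packs in 6.5.1 and 6.6.1.
2. Report post-insertion antibiotic use and admissions alongside, or split by, baseline status. With 25 per cohort the cells will be small, so a cross-tabulation is enough.
3. In 8.5, state that microbiology is summarised at Surgery 2 only, and that CFU counts in urine cannot distinguish new from carried-over colonisation.

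The cost is about one extra questionnaire page per participant, a few lines of analysis and a minor amendment.

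Optional, and not part of the core fix: a urine culture at Surgery 1 before insertion. That means about 50 more cultures (2 × 25), with changes to the schedule and Laboratory Manual and probably to the participant information. It is the only one of these steps that would inform carry-over in the CFU counts.
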